10.3.3 RCT Secondary Analysis Plan

The occurrence of CAI with a potentially susceptible partner in the last three months will be assessed at baseline, three-months, and six-months following the intervention. At each time point, participants will complete the web-based CASI survey that will include items on sexual risk behaviors over the prior three months. These items will ask about frequency of insertive and receptive anal intercourse, condom use, and number and HIV status of partners. CAI with a potentially susceptible partner will be defined as ≥ 1 act of condomless anal intercourse with a partner who is not known to be HIV-positive. To assess intervention effect at the time point of primary interest (six months), we will use a binomial regression model (with identity link) for the RD in any CAI with a susceptible partner (vs. none) at six months, comparing the intervention groups to the control group. Similar to viral suppression, we expect that the probability of CAI with a susceptible partner will be similar for intervention and control groups at baseline. We will use inverse probability of treatment weights to correct any imbalances in baseline CAI with a susceptible partner. In addition, baseline covariates may be included in the model to improve precision of treatment effects. Censoring weights may also be included if loss to follow-up exceeds 15% or if there is evidence of differential censoring by treatment group.

In addition to the main six-month CAI outcome (any CAI with a potentially susceptible partner in the last 3 months), we will conduct a separate analysis in which “potentially susceptible partner” is defined as a partner who is not known to be HIV-positive or taking HIV medications (including PrEP). Additionally, we will compare the intervention and control arms with respect to the number of CAI acts in the last three months according to partner HIV and PrEP status (known HIV-positive, HIV-negative and not on PrEP, HIV-negative and on PrEP, unknown HIV status). Finally, linear mixed models will be fitted to all continuous outcome measures (i.e., self-regulation, self-efficacy to disclose, disclosure outcome expectations, consequences of disclosure, and intentions to disclose) to estimate the relative change in mean response from baseline to 6 months between intervention and SOC groups. Before fitting all models we will look for balance between treatment arms to assess the success of randomization, and we will adjust for possible confounding variables to improve precision and validity where needed. In the event that loss to follow-up is differential across treatment arms, we will employ inverse probability weighting to correct for this selection bias. We will test hypotheses using the likelihood ratio test, and goodness-of-fit among models will be assessed using the likelihood-ratio test, AIC and BIC criteria. Intervention completion and acceptability will be assessed at 1 month, and sensitivity analyses will evaluate how our findings for primary outcomes are influenced when we account for observed intervention completion.

Transmission Model

We will use a modified Bernoulli process mathematical model²⁶ to estimate the expected number of secondary sexual HIV transmission events for study participants. The estimated number of transmissions expected from each participant in each three-month interval (months -3 to 0, months 1 to 3, months 4 to 6) will be based on his viral load, specific risk behaviors, reported numbers of partners and acts within those partnerships, and partner HIV/PrEP status in that interval. In addition to the study data, we will review the literature to obtain model parameters for per-act HIV transmission probabilities, the effect of viral load and condom use on transmission probabilities, and expected HIV prevalence among partners whose HIV status was unknown. To account for uncertainty in model input parameters, we will run 10,000 simulations of the model, varying the input values for parameters obtained from the literature. The main output of each model run is the expected number of secondary transmissions for each participant over the six months after baseline, which will be summarized as the mean value (with 95% credible interval) in that period across all simulations. We will compare the estimated transmission events for the intervention and control groups to estimate transmissions averted due to the Tough Talks approach.

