2.2 Secondary Outcomes

We will also assess intervention efficacy on a panel of self-reported outcomes including condomless anal intercourse (CAI), STI infections, and disclosure behaviors, intentions and self-efficacy. For binary outcomes, we define intervention efficacy as a difference in proportions, while for continuous outcomes, we define efficacy as a difference in means. (See Table 2 on page 45)

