5.3 Randomization Procedures

Participants will be randomized in a 1:1:1 ratio into either the Tough Talks fully online intervention, the Tough Talks clinic-based intervention, or the SOC control condition, based on a robust randomization sequence developed by UNC. The randomization sequence will be stratified by study site.

The randomization sequence will be setup in REDCap such that study staff may use the randomization feature to determine study arm assignment for each participant. Staff will not be aware of the randomization sequence, and therefore will not know what preceding or subsequent assignments will be.

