5.4.3 RCT

Recruitment for the RCT will occur from the 6 study sites (Tampa, FL; Houston, TX; Bronx, NY; Chapel Hill, NC; Atlanta, GA; Charlotte, NC), as well as through online channels such as social media. Identifying, screening and enrolling potential participants for the RCT will proceed as described in sections 4.3, 4.4, 4.5, and 5.1. After eligibility is confirmed, and consent/assent is obtained, participants will be assigned a study ID, complete the baseline CASI survey, and then be randomized to a study arm. Next, participants will be walked through a brief description of their study arm (clinic, at home, control). Participants will be compensated \$50-\$100 at the conclusion of the enrollment visit (depending on arm) and reminded

that they will be asked to complete follow up assessments online at one, three, and six months, in addition to a two week visit after enrollment for the in-clinic arm only.

The study team will conduct a combined efficacy/effectiveness trial to compare the intervention delivered online, in the clinic or SOC disclosure materials. Primary and secondary outcomes will be assessed at intervention completion (one month), three months, and at six months, and will include HIV VL information (abstracted via chart review, shared by participant via Qualtrics, or blood draw), self-report data based on the CASI surveys and staff completion of costing tools and CRFs. Mathematical modeling will estimate transmissions averted and costs of each arm.

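### The mixed models for the five continuous disclosure outcomes do not fix how the baseline score enters; fitted in the usual way they give a valid but less precise contrast than a common-baseline model

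*Combined protocol and SAP*

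**What the plan says.** The RCT Secondary Analysis Plan (section 10.3.3) covers five continuous measures: "self-regulation, self-efficacy to disclose, disclosure outcome expectations, consequences of disclosure, and intentions to disclose". Linear mixed models are to be fitted "to estimate the relative change in mean response from baseline to 6 months between intervention and SOC groups". The fixed effects, the covariance structure and the role of the baseline score are not given.

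On adjustment, the same section says "Before fitting all models we will look for balance between treatment arms to assess the success of randomization", and then "we will adjust for possible confounding variables to improve precision and validity where needed". The variables are not named.

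Section 2.2 says of secondary outcomes that "for continuous outcomes, we define efficacy as a difference in means". It gives no time point and does not choose between level and change.

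Section 5.4.3 has participants "complete the baseline CASI survey, and then be randomized to a study arm", and section 5.3 says "Participants will be randomized in a 1:1:1 ratio". Table 2 schedules these measures at baseline, one, three and six months.

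**The concern.** The planned sentence puts baseline at one end of the contrast. The model most analysts would fit has arm, time and arm-by-time effects, with the six-month interaction as the result. That model estimates a separate baseline mean in each arm, although the arms are random samples from one population when the baseline survey is taken. Estimating differences known to be zero adds their noise to the treatment contrast.

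These outcomes lie closest to what the app is meant to change, and section 10.2.3 gives power for viral suppression only. With no stated power for these outcomes, an avoidable loss of precision deserves attention. The open specification also lets an analyst choose between a change contrast, a six-month contrast and a baseline-adjusted contrast after seeing the data.

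**Working it through.** **The plan's own figure.** The only sample size in the documents is for viral suppression, 0.66 against 0.88. With pooled variance, two-sided 0.05 and 80% power, n = [1.960·√(2·0.77·0.23) + 0.842·√(0.66·0.34 + 0.88·0.12)]² / 0.22² = 56.2, and 56.2/0.85 = 66.2. The stated 66 per arm reproduces. It says nothing about the continuous outcomes, for which there is no plan figure to check.

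**Inputs.**
- From the documents: 66 per arm and 15% lost by six months (section 10.2.3); visits at 0, 1, 3 and 6 months (Table 2); baseline survey before randomisation (sections 3.3, 5.1 and 5.4.3).
- Assumed: cumulative dropout of 5%, 10% and 15% at months 1, 3 and 6; equal variances; compound symmetry with correlation r; a true effect of 0.5 SD for the power figures.

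**Complete-data formulas.** With n per arm and unit variance:
- difference in change, arm-specific baseline means: V = (2/n)·2(1 − r)
- common baseline mean, or baseline score as covariate: V = (2/n)·(1 − r²)
- ratio of the second to the first: (1 + r)/2, which is 0.65, 0.75, 0.85 and 0.95 at r = 0.3, 0.5, 0.7 and 0.9.

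**With four visits and dropout.** I computed the generalised least squares information matrices for both models. Power is Φ(0.5/√V − 1.960).

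| r | V, change contrast | V, common baseline | Ratio | Power, change | Power, common baseline |
|---|---|---|---|---|---|
| 0.3 | 0.0470 | 0.0322 | 0.68 | 63.5% | 79.6% |
| 0.5 | 0.0339 | 0.0263 | 0.78 | 77.5% | 86.9% |
| 0.7 | 0.0205 | 0.0178 | 0.87 | 93.7% | 96.3% |
| 0.9 | 0.0069 | 0.0066 | 0.96 | near 100% | near 100% |

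At r = 0.5, for example, 0.5/√0.0339 − 1.960 = 0.76, giving 77.5%, and 0.5/√0.0263 − 1.960 = 1.12, giving 86.9%. In participants, the gain equals 0.0470/0.0322 − 1 = 46% more at r = 0.3, 29% at 0.5, 15% at 0.7 and about 5% at 0.9.

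**Do the contrasts target the same quantity?** In a simulation with 400 replicates per correlation and a true six-month difference of 0.40 SD, at r = 0.3, 0.5 and 0.7, the average estimates were:
- difference in change: 0.39 to 0.41
- six-month difference: 0.38 to 0.39
- common-baseline estimate: 0.39 to 0.40

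All three agree with the truth within simulation error. The standard error of the change contrast was about 1.19, 1.12 and 1.07 times that of the common-baseline estimate, in line with the table.

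**The case against.** The strongest reply is that arm-specific baseline means appear nowhere in the documents. The plan names a model class and a contrast, and a common-baseline model also yields a between-arm difference in change. This stands: the loss is conditional on the usual parameterisation. But nothing in the plan selects the more precise model, and the plain reading leads to the less precise one.

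A second reply is that the plan already allows adjustment for precision. It does, but only where judged necessary after a balance check, and without naming the baseline score. For viral suppression and condomless anal intercourse, section 10.3.3 names the baseline value of the outcome as the imbalance to correct; for the continuous measures it does not. The clause therefore does not secure the gain.

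Third, every driver of the size except 66, 15% and the visit times is assumed. This also stands, and is why a range is given.

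Two stronger readings are tempting and are not supported:
- **That sections 2.2 and 10.3.3 define different estimands.** Baseline is measured before randomisation, so expected baseline means are equal and the difference in mean change equals the difference in six-month means. A difference in mean change is itself a difference in means.
- **That chance baseline gaps bias the result through regression to the mean.** A gap above 0.2 SD has probability of about 0.25, since its SD is √(2/66) = 0.174. Over randomisations, however, the change contrast is unbiased, and this variability is already in its standard error. It is the same precision loss described again.

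One check on the premise: the bulleted list in section 6.2.1 puts randomisation above the baseline survey. Sections 3.3, 5.1 and 5.4.3 all give the sequence in prose with the survey first, so I take that as the order.

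**Conclusion.** The point holds as a matter of precision and specification, not validity. If the mixed models are fitted with arm-specific baseline means and no adjustment for the baseline score, the six-month contrast is unbiased. Its variance, however, is larger than it need be: the common-baseline variance is 0.68 to 0.96 of it for correlations from 0.3 to 0.9. The power gain for a 0.5 SD effect is about 16 percentage points at 0.3 (79.6 − 63.5), 9 at 0.5 (86.9 − 77.5) and under 3 at 0.7 (96.3 − 93.7). The documents cannot say where these scales fall.

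Between sections 2.2 and 10.3.3 there is only loose wording: the first gives no time point, and the word *relative* in the second could be taken to mean a ratio. The primary outcome, its analysis and the stated sample size are unaffected.

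**What to change.** In the RCT Secondary Analysis Plan, state the mixed model in full:
- Fit baseline, one-, three- and six-month scores as responses, with time effects and arm-by-time effects at months 1, 3 and 6 only, and no arm main effect, so that all arms share one baseline mean. Alternatively, take the baseline score as a covariate for the follow-up scores.
- Do this in every case, not depending on the balance check.
- State the covariance structure.
- Name the result as the six-month arm-minus-SOC difference in means, in place of the present change wording, and add the six-month time point to section 2.2.

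The cost is a few sentences of analysis-plan text, best settled before unblinded analysis. No new data, visits, participants or software are needed.

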2.2.1 Cost Outcomes and Cost Effectiveness

To compare costs between the intervention arms, we will collect information on (1) time spent by study staff for training and supervision of delivering the clinic VR intervention; (2) time participants spend in the clinic sessions; and (3) costs associated with the delivery of both home and clinic arms. The procedures we will use to quantify the resources required to deliver the interventions will be organized in standard expenditure categories: personnel, supplies, equipment, services, space, and overhead. Incremental cost effectiveness ratio between the 2 intervention arms will be defined as $\Delta C/\Delta E$, where ΔC denotes the estimated difference in mean costs of the intervention and ΔE reflects the estimated difference in mean effectiveness of proportion suppressed between the interventions.

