6.5.2 Clinical Procedures

- Viral load measure, taken from chart (if within six weeks prior to or following three-month follow up)

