10.1.3 RCT

Conduct a combined efficacy/effectiveness trial to compare the intervention delivered online, in the clinic, or SOC clinic disclosure messaging. The primary outcome of HIV viral suppression will be assessed at six months. We will also assess intervention efficacy on a panel of self-reported outcomes including CAI, STI infections, disclosure behaviors, intentions and self-efficacy assessed at baseline, 3 months, and 6 months. Cost effectiveness of both intervention arms will also be assessed.

The primary analysis will be based on intention-to-treat principles, where all participants are assumed to have followed their randomized assignment; secondary analyses will account for observed intervention completion. Additionally, we will develop a mathematical model to estimate secondary HIV transmissions and potential transmissions averted as a result of the intervention's effect on viral suppression and CAI with susceptible partners.

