- 2) Emotional discomfort during the assessment and/or while using the mobile app. While participants will be informed that they may refuse to answer any questions at any time, responses or reactions to certain questions may indicate distress on the part of the participants. If at any time during the study, a participant divulges that he is at risk for harm, including but not limited to being abused or experiencing violence, if harm is suspected or likely, or if the participant states he is suicidal/homicidal, measures will be taken to ensure his safety locally. Reporting will be made as appropriate to the situation and the legal statutes, and referrals will be provided for appropriate support, counseling or treatment resources.

- 3) Discomfort during collection of blood specimen. Whenever possible, we will conduct a medical chart review in order to minimize the need for blood sample collection for participants. There are only two time points in the study that require a potential blood draw if VL is not provided in the participants' medical chart (enrollment and 6-month assessment). All necessary blood sample draws will be executed by trained professionals within the SRV sites or independent laboratory.

In addition to a Certificate of Confidentiality, we will protect participants in the following ways:

We will take every precaution to minimize risks to study participants. Adverse events will be reported to the UNC-CH IRB, individual research PI institutional IRBs, and STUDY site-specific IRBs per each institution's IRB reporting requirements using Adverse Event CRF. When possible, reports will be sent within 24 hours of notification by the PIs. Annual updates on enrollment and retention will also be sent to the IRBs.

All data collection will take place in secure and supervised clinical settings. All study personnel have completed training and received certification in Human Subjects Research Protection (CITI Program) and HIPAA regulations. They will continue to renew this training in compliance with the UNC IRB policy as well as their individual institutional policies.

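### Transmissions averted has no stated contrast or interval, and the transmission model's only interval reflects literature-parameter uncertainty alone

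*Combined protocol and SAP*

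**What the plan says.** The method appears once, under the Transmission Model subheading of section 10.3.3 (RCT Secondary Analysis Plan). Each participant's expected onward transmissions are computed from his own viral load, acts, partners and partner status, together with transmission parameters taken from published work. On uncertainty the plan says "we will run 10,000 simulations of the model, varying the input values for parameters obtained from the literature". It goes on: "The main output of each model run is the expected number of secondary transmissions for each participant over the six months after baseline", and this is "summarized as the mean value (with 95% credible interval) in that period across all simulations". The group comparison comes next and is a single sentence: "We will compare the estimated transmission events for the intervention and control groups to estimate transmissions averted due to the Tough Talks approach".

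Other sections give the aim without a method. Section 10.1.3 says "Additionally, we will develop a mathematical model to estimate secondary HIV transmissions and potential transmissions averted as a result of" the intervention's effect on suppression and on CAI with susceptible partners, and section 5.4.3 repeats the intention. Section 2.2 defines efficacy as a difference in means for continuous outcomes, but for the self-reported panel. The likelihood ratio test in section 10.3.3 belongs to the fitted regression and mixed models. Section 10.4 has nothing specific to this model.

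**The concern.** Every run uses the same participants. Only the published inputs change from run to run. The interval therefore shows how far the result depends on those inputs, given these men. Attributing averted transmissions to the intervention raises a second question: how much of the difference between randomised arms could be chance? No interval in the plan answers it.

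Three things are left open: the scale (total or per-person mean, difference or ratio), whether each intervention arm is compared with SOC or the two are pooled, and how the interval for the contrast is formed. The permitted choices behave very differently. A two-sample comparison of the participant-level outputs includes sampling error but no literature uncertainty. Taking the simulation interval across to the arm difference does the reverse. The certainty attached to a causally worded result would then depend on a choice made after the data are seen, and one available choice can present a chance difference as averted transmissions.

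**Working it through.** **1. Evaluable number.** Section 10.2.3 gives 66 per arm, 15% loss, two-sided alpha 0.05 and 80% power, with suppression 0.66 at baseline in all arms and 0.88 at six months in the intervention arms. Taking SOC to stay at 0.66 (an assumption, since no six-month SOC value is given), the pooled-variance formula is

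n = [1.96·√(2·0.77·0.23) + 0.8416·√(0.66·0.34 + 0.88·0.12)]² / 0.22² = 56.2, so 57 evaluable per arm.

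57 × 1.15 = 65.6, which gives the plan's 66; 57 / 0.85 = 67.1 gives 68. The plan's figure is reproduced to within two participants. Loss of 15% leaves 66 × 0.85 = 56.1, about 56 per arm. No power or precision figure is given for transmissions averted.

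**2. Sampling error at 56 per arm.** For suppression, one of the model's inputs, with SOC again assumed to be 0.66:

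0.22 ± 1.96·√(0.66·0.34/56 + 0.88·0.12/56) = 0.22 ± 0.150, or 0.070 to 0.370.

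This is an interval for suppression, not for transmissions averted. It shows the order of sampling error that the simulation interval leaves out.

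**3. Why a literature-only difference tends to exclude zero.** For a small per-act risk β, participant i's expected transmissions are roughly β·eᵢ, where eᵢ is his effective exposure. The arm difference is then about β·(ē_SOC − ē_arm). β is positive in every run. If only β varied, the observed participants would fix the sign and every run would fall on the same side of zero. Other literature inputs enter eᵢ, and the exact model is not linear, so the sign can change, but seldom.

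**4. Illustration.** The documents give no model inputs, so all are assumed. One intervention arm is compared with SOC, 56 participants each, with 400 trials × 300 draws per scenario. There are 18 base scenarios: negative-binomial acts with mean 8 or 20; dispersion 0.5, 1 or 3; SD of log per-act risk 0.2, 0.4 or 0.8. Each was run under 7 settings, changing one input at a time (any CAI 0.25, 0.40 or 0.60; mean per-act risk 0.003, 0.008 or 0.015; share of acts with unknown-status partners 0.25, 0.50 or 0.75), giving 18 × 7 = 126 scenarios. The effect of suppression was drawn from 0.90 to 1.00 and prevalence in unknown-status partners from 0.10 to 0.35. Identical arms had suppression 0.66 in both.

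| Interval or comparison for the arm difference | Zero excluded, identical arms | Coverage of true difference, 0.66 v 0.88 |
|---|---|---|
| Literature draws only, difference formed within each run | 87.5–97.5% | 19–83% (median 55%) |
| Literature draws only, separate draws for each arm | 0–61% | not tabulated |
| Non-overlap of the per-arm literature-only intervals | 0–46% | not tabulated |
| Welch comparison of participant-level means | 1–7% | 79–95% (median 90%) |
| One shared draw per run plus resampling within arm | 5–12% | 77–95% (median 91%) |

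At 0.66 v 0.88 the resampled interval was 1.3 to 4.9 times as wide as the within-run literature-only interval, and included zero in 53–83% of trials. A separately coded run on different assumed inputs gave 97–99% exclusion of zero with identical arms for the literature-only difference. Site strata and missing data were not simulated.

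**The case against.** The strongest reply is that the credible interval does what the plan says it does. The runs are there to account for uncertain inputs, and they do. The plan never says this interval will be used to judge whether the arms differ. That stands. A reader might infer that the trial will run a test with a false-positive rate near 90%; the documents state no such test, and the figure illustrates one permitted reading. It is also close to built in, as step 3 shows, once participants are held fixed.

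Second, because the model output is per participant, a two-sample comparison may be what the sponsor has in mind, and in the illustration it does about as well as resampling: lower exclusion of zero with identical arms and similar median coverage. Resampling had the clearer advantage only at the largest log-SD of 0.8 (coverage 86–95% against 79–90%). That also stands, and the simpler method is acceptable if named with its limit.

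Third, the output is peripheral. It is in none of the hypotheses of section 2.3, the outcomes of section 2.2 or Table 2, and the effect term of the cost-effectiveness ratio in section 2.2.1 is "the estimated difference in mean effectiveness of proportion suppressed between the interventions". This is conceded and sets the severity. It does not supply the missing contrast for a planned result that the text attributes to the intervention.

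A reader might also infer that month-3 viral loads will be lacking because no study draw is planned then. Sections 6.5.2 and 11.3.1 point that way, but the Clinical Samples entry of the Study Abstract and Table 2 list a blood draw as a source at three months. The documents conflict on this, and the point does not rest on it.

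**Conclusion.** The gap is certain on the text. Transmissions averted has no stated scale, pooling rule or interval, and the only interval in the transmission model is conditional on the participants observed. Severity is minor: the primary analysis, the listed secondary outcomes and the cost-effectiveness ratio are unaffected.

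The size is much less certain than the gap. That a literature-only arm difference will usually exclude zero when the arms are identical follows from holding the participants fixed. The figure of roughly 90% or more, and all the coverage and width figures, rest on assumed model inputs and show direction and rough scale only. The suppression interval of 0.070 to 0.370 rests on the assumption that SOC stays at 0.66.

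**What to change.** In the Transmission Model text of section 10.3.3:

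- Define transmissions averted as the difference in mean expected transmissions per participant over the six months after baseline, SOC minus each intervention arm.
- In each run, apply one draw of the literature parameters to all arms and resample participants with replacement within arm, within site where numbers allow because randomisation is stratified by site.
- Report the 2.5th to 97.5th percentiles of each difference as its interval, and label any literature-only interval as parameter uncertainty only.

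A two-sample comparison of participant-level means is an acceptable simpler alternative if the plan states that it omits literature-parameter uncertainty.

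The cost is two or three sentences in the plan and a little more code, with no new data. The interval will be wider and will often include zero. The percentile bootstrap is somewhat anti-conservative at this sample size (about 5–12% exclusion of zero with identical arms in the illustration, against a nominal 5%), and the plan should acknowledge this.
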